- 3) *Epistaxis Severity Score (ESS) ≥ 4 and 2 or more nosebleeds per week with a cumulative nosebleed duration of at least 5 minutes per week*
- 4) Stable nasal hygiene and medical regimen for preceding 1 month
- 5) Stable epistaxis pattern over the preceding 3 months

Exclusion Criteria:

- 1) Contraindications for systemic β adrenergic blocker administration
 - a. Hypersensitivity to β adrenergic blockers
 - b. Asthma or bronchospasm
 - c. Congestive heart failure with LVEF <40%
 - d. Hereditary pulmonary arterial hypertension
 - e. Baseline bradycardia (HR <55 beats per minute)
 - f. Sick Sinus Syndrome
 - g. 2nd or 3rd degree heart block, left or right bundle branch block, or bifascicular block
 - h. Uncontrolled diabetes mellitus (most recent HbA1c >9%) or diabetic ketoacidosis within last 6 months
 - i. Hypotension (systolic blood pressure < 90)
- 2) Known hypersensitivity to timolol
- 3) Severe peripheral circulatory disturbances (Raynaud phenomenon)
- 4) Known intermediate or poor metabolizer variant of the liver enzyme CYP2D6
- 5) Current use of any of the following known strong CYP2D6 inhibitors: fluoxetine (Prozac), paroxetine (Paxil), bupropion (Wellbutrin), quinidine, quinine, ritonavir (Norvir), and terbinafine (Lamisil)
- 6) Current use of the following other drugs known to pharmacodynamically interact with timolol: diltiazem, verapamil, digoxin, digitalis, propafenone, disopyramide, clonidine, flecainide, or lidocaine
- 7) Patients currently treated or who plan to initiate treatment with β -blockers
- 8) Use of any anti-angiogenic medication in the last month prior to recruitment, including bevacizumab, pazopanib, thalidomide, or lenalidomide
- 9) Illicit drug use, except marijuana
- 10) Known pheochromocytoma
- 11) Use of anticoagulants, antiplatelet, or fibrinolytic therapies within the last month prior to recruitment, except for low-dose (81 mg or less) of aspirin
- 12) Pregnancy or planned pregnancy in the next 6 months or currently breastfeeding
- 13) Inability to read or understand English

- 14) Inability to complete 8 weeks of therapy for any reason

Eligibility Determination

To determine potential eligibility for the study, the research team will query the medical record based on the following inclusion/exclusion criteria:

- Age (18 years or older)
- Medication history to assess current use of a β -blocker (exclusion)
- Allergy history to timolol (exclusion)
- Changes in epistaxis care in the last month (exclusion)

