Short Form (SF-36). The *Medical Outcomes Short Form-36 (SF-36)* was developed for use in clinical practice and research to measure general physical functional and quality of life. (Ware and Sherbourne 1992) The *SF-36* includes one multi-item scale that assesses eight health concepts: 1) limitations in physical activities because of health problems; 2) limitations in social activities because of physical or emotional problems; 3) limitations in usual role activities because of physical health problems; 4) bodily pain; 5) general mental health (psychological distress and well-being); 6) limitations in usual role activities because of emotional problems; 7) vitality (energy and fatigue); and 8) general health perceptions. See Appendix 4 for questionnaire.

Patient Satisfaction with Treatment. The *Treatment Satisfaction Questionnaire for Medication Version II (TSQMII)* is an 11-question questionnaire adapted and validated from the TSQM v. I in order to more precisely collect information (fewer questions and more consistent wording) regarding four general topics of patient satisfaction with treatment: effectiveness, side effects, convenience, and overall satisfaction. (See Appendix 5 questionnaire) (Atkinson et al. 2005; Atkinson et al. 2004)

Clinical Global Impression Scale (CGI). The overall response to treatment will be measured with the *Clinical Global Impression (CGI)* scale. The *CGI* Scale measures response to treatment for a number of disorders and has good internal consistency and validity. (Dunlop, Gray, and Rapaport 2017) Upon completion of the study, subjects will be asked to answer the following question: "Overall, how would you rate your response to treatment?" Response options are: *Very Much Improved, Much Improved, Minimally Improved, No Change, Minimally Worse, Much Worse, and Very Much Worse.*

Epistaxis, Transfusion, and Compliance (ETC) Logs. Patients will be asked to use the Cure HHT app from the online app store if they have a mobile device capable of this feature. It will include a daily reminder to track epistaxis frequency and severity, energy levels, if they received a blood transfusion and/or iron transfusion, and if they took their medication. If the patient answers yes to the transfusion, he or she will be prompted to describe the details of the transfusion, including quantity of units received. The app can directly share the information with the study team at the patient's request.

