If patients are not able to use the app for any reason, a text message and/or email will be sent to the patient each evening via the REDCap™ (Research Electronic Database) website that will ask questions about the frequency and severity of epistaxis and energy level that replicates the Cure HHT app. The REDCap™

survey will assess for compliance by asking if the research subject has used the assigned treatment that day. Once each week, the survey will ask the subject if he or she received a blood transfusion that week. REDCap™ is a password-protected site that will keep the information confidential.

Methods

Demographic information, including age, gender, and race, will be collected from each enrolled patient. Data will be collected regarding the duration of each patient's epistaxis history, previous treatments, and estimation of the average number of nosebleeds per day; HHT treatment history; co-morbid conditions, such as hypertension, inhalant allergies, and other blood dyscrasias; risk factors, such as cigarette smoking, use of CPAP, and use of supplemental oxygen; and medications associated with increased bleeding.

At the initial visit, research subjects will complete the informed consent process, *SF-36*, *ESS*, baseline electrocardiogram (ECG), CYP2D6 enzyme allele, blood pressure (BP), and heart rate (HR). ECGs are to be read by [name]. Subjects will undergo a directed otolaryngology physical exam by [name] that will include nasal endoscopy to describe nasal mucosa telangiectasias. [name] will rate the nasal mucosa telangiectasias using the *HES*. Patients will be scheduled for phlebotomy to obtain a blood specimen to measure hemoglobin levels prior to beginning therapy. Baseline daily iron supplementation will also be recorded and it will be recommended to the patient not to alter their daily supplementation of iron or other treatments, unless indicated by a change in epistaxis frequency.

Upon demonstration that patient does not have the CYP2D6 allele associated with a low or intermediate metabolizer of timolol and successful completion of questionnaires, physical examination, and laboratory tests, subjects will be randomized to receive either timolol gel or placebo.

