Pharmaceutical Preparation. The intervention will be prepared and dispensed by Advanced Rx Pharmacy, Plymouth Meeting, Pennsylvania. Timolol nasal gel 0.1% will be prepared with a poloxamer gel (combination of poloxamer 188 and 407; pH adjusted to 4.5-6.5) and 0.5 ml applied to each nostril twice daily. The total daily dose would amount to 2 mg. Placebo gel is prepared with poloxamers and no active ingredients. Timolol is odorless so the research subjects should not be able to identify the placebo gel from the active gel.

Subjects will be instructed to apply 0.5 ml to the nasal mucosa of each nostril twice daily via 20 mL syringes. The gel will be dispensed in an amber vial with an adapter to which the syringe can attach in order to draw out the medication for each dose. Patients will be supplied with one syringe per day for a total of 56 syringes. They will be given alcohol wipes to clean the syringe between the morning and evening gel application. When the syringes are distributed, the research assistants will make sure that the patient understands how to apply correctly the medication to the nasal cavity.

BP and HR measurements will be obtained by the subject weekly at home with the use of the blood pressure monitor given to them at the beginning of the study and blood pressures will be reported via the use of REDCap™. Subjects will also be instructed to report any local or systemic side effects throughout the duration of the study. Telephone calls with the study team at the end of Week 1 and again at Week 4 will be arranged.

After 8 weeks of intervention, subjects will be asked to return to clinic and the physician will perform nasal endoscopy and complete the *HES* scale. Subjects will have blood pressure and heart rate measurements. Subjects will complete the *SF-36*, *ESS*, *CGI*, *EQQoL*, and the *TSQMII* questionnaires. To assess the quality of the blind, subjects will be asked which arm of the study they thought they were randomized. Subjects

will also be asked whether they would recommend the treatment to a friend or family member if they suffered with HHT-associated epistaxis. A follow-up blood draw to measure hemoglobin and hematocrit will be completed.

It will be emphasized to the patient not to change their current nasal hygiene regimen (e.g., nasal saline spray) or other chronic treatments (e.g., tranexamic acid).

[figure not shown]
Primary Outcome:

- 1) Mean change in Epistaxis Severity Score (ESS) between baseline and follow-up.

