Secondary Outcomes:

- 1) Clinical Global Impression – Improvement (CGI-I) Score
- 2) Mean change in hemoglobin
- 3) Change in intensity of telangiectasias in the nasal mucosa as determined by the HHT endoscopic scale (HES)

Summary of Project Design

VIII. SAMPLE SIZE AND PLANNED STATISTICAL ANALYSIS

Sample Size

Sample size estimate for the proposed study were derived from the single study(Ichimura et al. 2016) of within subject change in severity of epistaxis associated with timolol ophthalmic solution (0.5%) as a nasal drop. In that study, 9 of the 11 subjects (82%) experienced a reduction in the severity of bleeds as measured on a 5-point Likert scale. We hypothesize a similar response (82%) in our proposed study among subjects randomized to receive timolol gel and a 20% response rate among subjects randomized to placebo gel, corresponding to a difference of 62%.

A power analysis was performed using Fisher’s exact test in G-Power 3.1.2. We estimate that a total sample size of 24 patients (ie., 12 in each arm) is needed to allow us to detect with 80% power at the 2-sided alpha level of 0.05 a difference of 62% or more in the percent of subjects who experience reduction of severity of

bleeds between treatment groups. Considering a 20% drop out rate, we plan to enroll 30 subjects in the study.

Statistical Analysis

Standard descriptive statistics will be used to describe distribution of baseline characteristics in each of the study groups. The effect of the intervention will be measured as the difference in the within-subject change (baseline – 8-week follow-up) in *ESS* scores between the two treatment groups calculated as shown below.

1) Within subject difference with each treatment group

$$\begin{aligned}\Delta ESS_{\text{Timolol}} &= (ESS_{\text{Timolol_base}} - ESS_{\text{Timolol_8-Week}}) \\ \Delta ESS_{\text{Control}} &= (ESS_{\text{Timolol_base}} - ESS_{\text{Timolol_8-Week}})\end{aligned}$$

2) Between treatment difference

$$\Delta ESS_{\text{Timolol}} - \Delta ESS_{\text{Control}}$$

The 95%CI around this effect size will be determined to assess the precision of the observed effect and whether a clinically meaningful difference is plausible given the observed results.

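### Exclusion criteria 5 and 6 bar only current use of 16 interacting drugs, so a patient known at screening to be due to start one is not excluded by them, and no contact in the visible text asks about new drugs

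*Combined protocol and SAP*

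**What the plan says.** The three drug-related criteria stand next to each other in Section VII, Exclusion Criteria.

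- Criterion 5: "Current use of any of the following known strong CYP2D6 inhibitors", followed by seven drugs.
- Criterion 6: "Current use of the following other drugs known to pharmacodynamically interact with timolol", followed by nine drugs.
- Criterion 7: "Patients currently treated or who plan to initiate treatment with" beta-blockers.

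During treatment, the instructions on other therapy are general. At baseline, "it will be recommended to the patient not to alter their daily supplementation of iron or other treatments", with an exception if epistaxis frequency changes. The end of the Methods text repeats the message for the nasal hygiene regimen "or other chronic treatments (e.g., tranexamic acid" being the example given for the latter).

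The contacts after dispensing are described in Section VII (ETC Logs, Methods) and Section X. For the app log, "It will include a daily reminder to track epistaxis frequency and severity, energy levels", together with transfusions and use of the study gel. Subjects report blood pressure, heart rate and side effects weekly, and are telephoned at the end of Weeks 1 and 4. Finally, "After 8 weeks of intervention, subjects will be asked to return to clinic" for endoscopy, vital signs, questionnaires and a blood draw.

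**The concern.** The sponsor used forward-looking wording where it wanted it: criterion 7 covers planned beta-blocker treatment and criterion 12 covers planned pregnancy. Criteria 5 and 6 lack it, although they list drugs that the sponsor regards as unsuitable alongside timolol.

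The protocol's own reasoning shows why timing matters. Section X ties both timolol plasma levels and the frequency of adverse events to CYP2D6 phenotype, and every subject is genotyped for that reason. Genotype is tested once, before randomization. A strong CYP2D6 inhibitor started afterwards undercuts that safeguard in a subject who passed it. Criterion 6 drugs are a separate hazard, because genotyping says nothing about a pharmacodynamic interaction.

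At stake is the prevention of an avoidable exposure in individual subjects. A prospective record would also help: Aim 3 is the safety profile, and a bradycardia event is harder to attribute if the start date of an interacting drug was never collected.

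**Working it through.** No figure in the plan bears on this point, so the check is a count and a comparison of texts.

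**1. Drugs with the narrower time scope (Section VII, Exclusion Criteria).**
- Criterion 5: fluoxetine, paroxetine, bupropion, quinidine, quinine, ritonavir, terbinafine = 7.
- Criterion 6: diltiazem, verapamil, digoxin, digitalis, propafenone, disopyramide, clonidine, flecainide, lidocaine = 9.
- No name appears twice, so 7 + 9 = 16.

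**2. Does another criterion exclude a planned start of one of these 16?**
- Inclusion 4 requires a stable regimen, but only over the month before entry. A start due in week 2 does not breach it.
- Exclusion 7 looks forward, but only for beta-blockers. None of the 16 is a beta-blocker.
- Exclusion 14 concerns patients who cannot complete 8 weeks of therapy. An investigator could apply it to someone whose planned drug would force the gel to stop. It does not say so, and such a patient may be able to complete therapy.

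None of these makes the patient clearly ineligible.

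**3. Does a scheduled contact ask about new drugs?** There are four types of contact, or five scheduled items if the two calls are counted separately.
- Daily log, by app or by REDCap: epistaxis, energy, transfusion and use of study gel. No question on other drugs.
- Weekly report: blood pressure, heart rate and side effects. No question on other drugs.
- Week 1 and Week 4 calls: questions or concerns, side effects, and changes in iron supplementation or transfusion pattern. Treatment changes are asked about, but not the listed drugs.
- Week-8 visit: endoscopy, vital signs, questionnaires, the guess at treatment arm, whether the subject would recommend the treatment, and a blood draw. No medication question is listed.

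**4. Limits of step 3.** A figure follows the description of the week-8 visit and is not shown, nothing is visible under Summary of Project Design, and the case report forms are not available. Step 3 is therefore a statement about the visible text. Steps 1 and 2 rest on the complete list of criteria and do not have this limit.

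**The case against.** The best counter-argument is that several provisions already cover this case. Subjects are told not to change other treatments, and a general instruction need not name drugs. Exclusion 14 gives the investigator some room. Telephone help is available around the clock (Section XII), and the calls invite concerns. The stopping rules in Section X act on an asymptomatic systolic fall (below 80 mmHg, or 20% from baseline) and on a heart rate below 50 with no symptom required; a physician may also stop treatment as unsafe. The daily dose is 2 mg, against 6 mg in the case report of bradycardia in an intermediate metabolizer, and one arm receives placebo.

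Much of this stands, and it is why the point is minor. But the instruction's examples are iron, saline spray and tranexamic acid. A newly prescribed antidepressant is not obviously a change to an existing chronic treatment. Nor does the instruction affect eligibility or record a start. Weekly readings can miss a rapid effect: in the cited prospective timolol study one patient had hypotension and bradycardia on the second day.

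Four stronger readings are tempting and not supported.
- A reader might infer that the trial collects no information on concomitant drugs at all. The missing figure and forms rule out that conclusion.
- A reader might infer that harm would be noticed only once it had happened. The asymptomatic blood pressure and heart rate rules can act earlier.
- A reader might infer that an inhibitor raises exposure 2.5-fold. That figure compares poor with extensive metabolizers after 0.5% aqueous eye drops; the documents do not quantify an inhibitor's effect with this gel.
- A reader might infer a threat to the sample size. No rate of new starts is given, and no such effect can be derived.

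**Conclusion.** The point holds as a minor matter of patient safety and eligibility wording. Sixteen named drugs have a narrower time scope in criteria 5 and 6 than beta-blockers have in criterion 7, and following the criteria exactly admits a patient with a known planned start. That part is firm. The absence of a new-medication question holds for the visible text only.

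The number of subjects affected cannot be estimated, because the documents give no start rate for these drugs. The scenario is narrow for criteria 5 and 6 themselves (a start already planned at screening, falling within 8 weeks) and somewhat wider for the missing question, which would also pick up unplanned starts. No effect on power, error rate or the between-arm comparison is claimed.

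**What to change.** 1. Extend criteria 5 and 6 to *current use or planned start before the week-8 visit*.
2. Add one yes/no new-medication item, with start date, to the existing weekly report and to the week-8 visit. This covers unplanned starts, which the first change cannot.
3. Ask subjects to tell the study team promptly if a drug listed in criterion 5 or 6, or a beta-blocker, is prescribed, so that the study physician can hold or stop the gel. The request should say plainly that indicated treatment must not be delayed; it is the gel that gives way.

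The cost is a phrase in two criteria, one item on a report and a visit that already exist, and one instruction. The downside is possibly a few more screen failures and a few subjects whose gel is held, including some on placebo because the physician is blinded. The documents give no rate for either.

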Assisted Epistaxis Severity Score (aESS). Assessment of epistaxis severity will be obtained by the validated instrument, the *Epistaxis Severity Score (ESS)*. (Hoag et al. 2010) (Appendix 1) To complete the *ESS*, patients are asked to consider typical symptoms over the previous 3 months. However, with the 8-week duration of our trial, patients will complete the *aESS* in reference to their epistaxis over the past 1 month. The *ESS* contains 6 items – frequency, duration, and intensity of nosebleeds, whether patient has

sought medication attention, whether patient is anemic, and whether patient has received a blood transfusion. The overall score ranges from 0 to 10, with severity of nosebleed based on score graded as *None* composite score of 0-1, *Mild* 1-4, *Moderate* 4-7, and *Severe* as 7-10. The minimal important difference noticeable by both patients and clinicians in the ESS scoring system is estimated as a change of 0.71. (Yin et al. 2016)

HHT Endoscopy Score (HES). The *HHT Endoscopy Score (HES)* is an endoscopy staging score developed as a way to quantify the severity of the patient's nasal telangiectasias as seen on physical exam. (Reh et al. 2014) The *HES* was shown to correlate with the *ESS*. Its parameters are telangiectasia sites, patterns, crusting, location, perforation, density, and relative AVMs. Scoring of the HES is illustrated in Appendix 2.

Epistaxis-Specific Quality-Of-Life Questionnaire (EQQoL). The EQQoL measures 13 items that focus on the impact of epistaxis on the patient's physical, functional, and emotional status and quality of life. (Ingrand et al. 2011) The EQQoL was shown to have satisfactory psychometric properties and when combined with the SF-36 measures both disease-specific and general quality of life. See Appendix 3 for questionnaire.

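### The only baseline ESS listed is taken at the initial visit, with no limit on the wait to first dose and no repeat, so the change score loses some precision that one short form could recover

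*Combined protocol and SAP*

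**What the plan says.** Section VII, Methods, puts the baseline score at the first contact: "At the initial visit, research subjects will complete the informed consent process, *SF-36*, *ESS*, baseline electrocardiogram (ECG), CYP2D6 enzyme allele". Hemoglobin is handled separately: "Patients will be scheduled for phlebotomy to obtain a blood specimen to measure hemoglobin levels prior to beginning therapy". Randomization follows the genotype result and completion of the other assessments: "Upon demonstration that patient does not have the CYP2D6 allele associated with a low or intermediate metabolizer of timolol and successful completion of questionnaires". Under Pharmaceutical Preparation, "The intervention will be prepared and dispensed by Advanced Rx Pharmacy", an outside supplier. The same subsection mentions a hand-over: "When the syringes are distributed, the research assistants will make sure that the patient understands how to apply correctly the medication". It does not say when that happens or whether it is a separate visit.

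The recall period is shortened for this trial (Section VII, Variables Under Study): "patients will complete the *aESS* in reference to their epistaxis over the past 1 month". The inclusion criteria require ESS of at least 4, "Stable nasal hygiene and medical regimen for preceding 1 month", and a stable bleeding pattern for three months. The next ESS listed is the one after 8 weeks.

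Section VIII, Statistical Analysis, defines the effect as the between-arm difference in baseline minus 8-week ESS and tests it with an independent-sample t-test. Adjustment is planned only if confounders are identified, and baseline ESS is not named as a covariate. The design figure is not shown in the extracted text and may give timing.

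**The concern.** Three steps stand between the baseline score and the first dose: a laboratory result, randomization and external dispensing. With a one-month recall, each week of waiting removes about a quarter of the last four pre-treatment weeks from what the score describes. The text neither limits the wait nor takes a second score.

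The primary variable is a raw difference from that single score, so both its measurement error and any drift before the first dose enter the outcome in full, in both arms. The plan intends to use the 95% CI to judge precision and whether a clinically meaningful difference is plausible. With the SDs of the earlier propranolol gel trial (Section V, Recent Study) and 12 per arm, the CI half-width is 2.074 × 1.329 × √(2/12) = 1.12 points, against a minimal important difference of 0.71. A trial this small has little precision to give away.

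**Working it through.** **The plan's own figure.** Section VIII gives 24 subjects for 82% versus 20% responders with Fisher's exact test, two-sided 0.05. Exact enumeration gives power of 77.4% at 11 per arm and 84.5% at 12, so 12 per arm is confirmed, and 24/0.8 = 30 to enroll. This calculation uses a binary endpoint, so it neither supports nor weakens the present point. The change-score analysis has to be examined separately.

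**Coverage of the pre-treatment month.** Taking one month as 4 weeks, coverage = max(0, (4 − gap)/4):

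| Gap to first dose (weeks) | Share of last 4 weeks covered |
|---|---|
| 0 | 100% |
| 1 | 75% |
| 2 | 50% |
| 3 | 25% |
| 4 or more | 0% |

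The documents do not give the gap, so the row that applies is unknown. If waiting lowered the baseline to week-8 correlation from 0.70 to 0.65 or 0.60 (assumed), the SD of change would rise by √(0.35/0.30) − 1 = 8% or √(0.40/0.30) − 1 = 15%.

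**Inputs for the gain from a second score.**
- Change SDs of 1.7 (active) and 0.8 (placebo) and a difference of 1.55, from Section V, Recent Study.
- Pooled variance (1.7² + 0.8²)/2 = 1.765, pooled SD 1.329, d = 1.55/1.329 = 1.17.
- Assumed, not in the documents: r (baseline to week 8) = 0.6 to 0.7, and rb (between the two baseline scores) = 0.9, high because their recall windows would overlap over a short wait. Equal variances at each time.

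**Change-score analysis.** With score variance s², one baseline gives a change variance of 2s²(1 − r). Using the mean of two baselines gives s²[(1 + rb)/2 + 1 − 2r]. The proportional cut is (1 − rb)/(4(1 − r)):
- r = 0.6: 0.1/1.6 = 6.3%
- r = 0.7: 0.1/1.2 = 8.3%

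Noncentral-t power at 12 per arm is 78.0% with one baseline. It is 80.5% after a 6.3% cut and 81.4% after an 8.3% cut. In subjects, 24/(1 − cut) − 24 = 1.6 to 2.2.

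**Scaled to the placebo arm.** Baseline error should be the same in both arms, and the larger active-arm SD may partly reflect varied response to treatment. Applying the cut to the placebo variance (0.8² = 0.64) gives an absolute reduction of 0.040 to 0.053, which is 2.3 to 3.0% of 1.765. Power becomes 78.9 to 79.2%, worth 0.6 to 0.8 subjects.

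**If ANCOVA is used.** Residual variance is s²(1 − r²) with one baseline and s²[1 − r²/((1 + rb)/2)] with the mean of two. At rb = 0.9:
- r = 0.6: from 0.640s² to 0.621s², a cut of 3.0%
- r = 0.7: from 0.510s² to 0.484s², a cut of 5.1%

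At r = rb = 0.7 the cut reaches 17%. On the pooled SD, ANCOVA with the existing single baseline multiplies the change variance by (1 + r)/2 and gives power of 86.3% (r = 0.6) or 84.2% (r = 0.7). The second score raises these to 87.3% and 86.0%. Scaled to the placebo arm, these gains would be smaller too.

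**The case against.** The strongest reply is that this is a generic case for replicate baselines. A single score has measurement error even on the day of first dose, and most of the computed gain would exist with no wait at all. That stands: the wait only adds to the error, by an amount that cannot be computed.

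The plan also has safeguards. Three months of stable epistaxis, a stable regimen and advice not to change treatments all limit drift over a short wait. They do not reduce measurement error.

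ANCOVA on the existing baseline needs no new data and, on the pooled SD, gains more than the second score does. That also stands. The second score adds a little to ANCOVA and does not replace it.

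Syringe distribution may coincide with the initial visit, since the text does not date it. The fix should therefore not depend on a separate contact there.

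A reader might infer that the baseline fails to describe the month before treatment. That would need a wait of four weeks or more. No interval is stated, and a shorter wait leaves partial overlap. A reader might also infer bias from the wait or from the ESS entry threshold. Both act before randomization and equally in expectation in the two arms, so regression to the mean inflates the within-arm improvement but not the expected between-arm difference.

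**Conclusion.** The point holds as a modest loss of precision. The readable text has one pre-treatment ESS, no limit on the interval to first dose and no repeat, and the unadjusted change score carries all the error in that one value. Validity is not in question.

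A second score would cut the change variance by about 6 to 8%, or 2 to 3% on the placebo-arm scale, moving power at 12 per arm from 78% to about 79 to 81%. This rests on r = 0.6 to 0.7, rb about 0.9, and SDs and an effect borrowed from a small trial of a different beta-blocker gel.

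Larger gains should not be claimed. A 25% cut with 88% power needs rb = r = 0.7, meaning that two largely overlapping recall windows agree no better than baseline and week 8 do. A longer wait would lower rb and make the second score more useful, but its length is not given. The design figure may also settle part of the timing. The change is worth making because it costs so little.

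**What to change.** Repeat the six-item aESS shortly before the first dose. Collect it at syringe distribution if that is a later contact than the initial visit, or otherwise through the REDCap survey system already planned for diaries and home blood pressure. Keep the initial score for eligibility.

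State in Section VIII that the analysis baseline is the mean of the two scores for every subject. A single definition avoids a primary variable that differs between subjects according to how long they waited. Preferably, analyze week-8 ESS by ANCOVA with that baseline as a prespecified covariate in place of the unadjusted t-test on change.

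The cost is one more short form per subject and a sentence or two in the analysis section.
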